#### **4.6.2.2 Number of infusions of CSL627 required to achieve hemostasis (1, 2, 3, or >3)**

[figure not shown]
The number of bleeding episodes and the number of treated bleeds, the number and the percentages of subjects with  $\geq 1$  bleeding episodes and with  $\geq 1$  treated bleeding episodes will be presented.

The number and percentage of bleeding episodes requiring 1, 2, 3 or more than 3 infusions of CSL627 to achieve hemostasis will be summarized using frequency counts and percentages. No statistical inference will be performed on this data.

In addition, the following parameters will be presented:

- Total dose per bleeding episode in IU and IU/Kg:
  - calculated as: sum of doses (IU) per bleeding episode;
  - calculated as: sum of doses (IU/Kg) per bleeding episode;
- Total dose per injection per bleeding episode in IU and IU/Kg:
  - i.e. total dose (IU) per injection given for any bleeding episodes;
  - i.e. total dose (IU/Kg) per injection given for any bleeding episode.

Treatment Success to achieve hemostasis will be as illustrated:

#### 4.6.2.3 Consumption of rVIII-SingleChain

Consumption will be summarized as described in [Section 4.1](#). Consumption will be summarized for the Efficacy population and Safety population. The following parameters will be derived and summarized using frequency counts or descriptive statistics for subjects on the routine prophylaxis regimen:

- Total number of prophylaxis injections overall calculated as sum of all prophylaxis injections including all subjects;
- Prophylaxis dose administered per subject per month and per year (IU/kg):
  - per year calculated as: sum of prophylaxis doses (IU/kg) per subject\*365.25/(efficacy evaluation period);
  - per month calculated as: sum of prophylaxis doses (IU/kg) per subject\*(365.25/12)/(efficacy evaluation period);
- Total dose administered per subject per month and per year (IU/kg):
  - per year calculated as: sum of doses (IU/kg) per subject\*365.25/(efficacy evaluation period);
  - per month calculated as: sum of doses (IU/kg) per subject\*(365.25/12)/(efficacy evaluation period);
- Prophylaxis IU administered per subject per month and per year (IU):

- per year calculated as:  $\text{sum of prophylaxis doses (IU) per subject} \times 365.25 / (\text{efficacy evaluation period})$ ;
- per month calculated as:  $\text{sum of prophylaxis doses (IU) per subject} \times (365.25/12) / (\text{efficacy evaluation period})$ ;
- Total IU administered per subject per month and per year (IU):
  - per year calculated as:  $\text{sum of doses (IU) per subject} \times 365.25 / (\text{efficacy evaluation period})$ ;
  - per month calculated as:  $\text{sum of doses (IU) per subject} \times (365.25/12) / (\text{efficacy evaluation period})$ .

Each dose (IU/kg) will be calculated using the total international units (IU) recorded and the most recent recorded value of weight (kg).

The following prophylaxis regimens will be presented for consumption during routine prophylaxis:

- Three times per week
- Two times per week
- All frequencies.

Prophylaxis infusions are those recorded as administered for 'Routine/Prophylaxis'. Total infusions also include those recorded as administered for 'Bleeding Event', 'Surgery', 'Post Surgery', 'Prevention Prior to Activity', and 'Additional Treatment'.

The following parameters will be derived and summarized using frequency counts or descriptive statistics for subjects assigned to on-demand treatment:

- Number of infusions per subject per month and per year:
  - per year calculated as:  $\text{sum of infusions per subject} \times 365.25 / (\text{efficacy evaluation period})$ ;
  - per month calculated as:  $\text{sum of infusions per subject} \times (365.25/12) / (\text{efficacy evaluation period})$ ;
- Total dose administered per subject per month and per year (IU/kg):
  - per year calculated as:  $\text{sum of doses (IU/kg) per subject} \times 365.25 / (\text{efficacy evaluation period})$ ;
  - per month calculated as:  $\text{sum of doses (IU/kg) per subject} \times (365.25/12) / (\text{efficacy evaluation period})$ ;
- Total IU administered per subject per month and per year (IU):
  - per year calculated as:  $\text{sum of doses (IU) per subject} \times 365.25 / (\text{efficacy evaluation period})$ ;
  - per month calculated as:  $\text{sum of doses (IU) per subject} \times (365.25/12) / (\text{efficacy evaluation period})$ .

Each dose (IU/kg) will be calculated using the total international units (IU) recorded and the most recent recorded value of weight (kg).

A specific analysis will be produced for consumption of rVIII-SingleChain while subjects are inhibitor positive on PUPs.

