- M:** If not available in subject's medical records, FVIII activity level must be determined at Screening at the local laboratory, and the result must be available before enrollment.
- N:** Virology retention samples: At Visit 1, the sample must be taken before first rVIII-SingleChain injection. CSL will retain samples for 5 years from EOS.
- O:** At Visit 1, the investigator will administer first rVIII-SingleChain dose after screening assessments are completed and subject eligibility is confirmed. Subject must be observed at the clinic for at least 6 hours after dosing.
- P:** Switches to the on-demand regimen and between various prophylaxis regimens are allowed at any time at discretion of the investigator. The eCRF should be updated accordingly for each switch. Subjects **switching to on-demand** should maintain their originally assigned visit schedule.
- Q:** Unused vials near expiration or with insufficient shelf life to cover time duration until next visit should be returned at the next scheduled visit. All unused vials will be returned at the EOS visit.
- R:** The observation period for adverse event (and serious adverse event) reporting in an individual subject will start at the time of giving written informed consent for participation in the current study and finish with the EOS visit. However, adverse events ongoing at the EOS visit will be followed until resolution or 28 days after the final administration of rVIII-SingleChain during this study, whichever is sooner.

CCI

Schedule of Assessments for Arm 2 PUPs WITHOUT Bleeding Episode at Screening and Assigned to ON-DEMAND

Assessments	Visits	Screening (up to 28 days before Visit 1)	Visit 1	Follow-up visits 1 month (± 7 days) after each rVIII-SingleChain dose ^{A,C,E}	Monthly phone calls (± 7 days) if duration between visits is > 1 month ^{B,C,E}	EOS ^D
Informed consent / assent		X				
Review of inclusion / exclusion criteria; subject eligibility		X	X ^F			
Demographic information		X				
Medical and surgical history		X				
Hemophilia A history (blood group, gene defect)		X				
Hemophilia A social history and activity level		X	X	X		X
Review of prior medications (previous 28 days)		X				
Blood sample for gene defect ^G		← At any time ^G →				
Serum chemistry and hematology ^H		X		X		X
CD4 lymphocyte count (for HIV+ subjects) ^I		X				
Vital signs		X	X ^J	X		X
Physical examination		X		X		X
Body weight and height		X	X	X		X
Inhibitor to FVIII ^L		X ^K		X ^U		X

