### 3.2 Study Treatment Dosing Regimen

In all study arms, the investigator will assign subjects to either prophylaxis or on-demand treatment regimens with rVIII-SingleChain. All subjects will be dosed according to the actual potency printed on the vial label and will be treated by IV injection. On-demand and prophylaxis doses can be adjusted as necessary at the discretion of the investigator. In all study arms, changes in treatment regimens (on-demand or prophylaxis) and dose modifications are allowed and are permitted at the investigator's discretion.

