### 3.2.6 Change in Treatment Regimens and Dose Modifications

In all study arms, changes in treatment regimens (on-demand or prophylaxis) and dose modifications are allowed and will be permitted at the investigator's discretion. The timing of dose adjustment should be flexible and based on the type of bleeding episode, the location of the bleeding episode, the age of the subject, and bleeding phenotype.

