## 4.6 Efficacy Analysis

The efficacy endpoints will be summarized and analyzed for the Efficacy population unless otherwise specified. The surgery substudy efficacy data will be summarized for the Surgery population. Efficacy analyses will be performed separately for the PTPs and PUPs and by modality. Efficacy results for the PUPs will be presented by inhibitor status (positive, negative) and overall.

The efficacy evaluation period begins on Treatment Day 1 date in this study and ends at the End of study Visit in this study or the last date of dose, whichever occurs later. Only those treated bleeding episodes and doses which fall within the efficacy evaluation period will count

towards the efficacy evaluation. The summary statistics to be presented are described in [Section 4.1](#).

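### Prophylaxis consumption per month and per year is divided by the whole efficacy evaluation period, so it is understated for subjects in the prophylaxis table who spent part of that period on-demand, and the SAP has no rule for classifying switchers

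*SAP*

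**What the plan says.** SAP 4.6.2.3 gives two sets of consumption formulas.

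- The first set is "for subjects on the routine prophylaxis regimen". The yearly figure is "sum of prophylaxis doses (IU/kg) per subject\*365.25/(efficacy evaluation period") and the monthly figure is "sum of prophylaxis doses (IU/kg) per subject\*(365.25/12)/(efficacy evaluation period"), with parallel formulas in IU. The numerator is restricted: "Prophylaxis infusions are those recorded as administered for 'Routine/Prophylaxis"'. Results are shown for three-times-weekly, twice-weekly and all frequencies. Total dose per month and year, for all reasons of use, is given alongside.
- The second set is for subjects assigned to on-demand treatment. It sums all infusions and all doses per subject and divides by the same period.

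SAP 4.6 defines the denominator: "The efficacy evaluation period begins on Treatment Day 1 date in this study and ends at the End of study Visit in this study", or at the last dose if that is later. It does not divide this period by modality or frequency, and it does not remove surgical time.

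Switching is part of the design. SAP 3.2 states that "changes in treatment regimens (on-demand or prophylaxis) and dose modifications are allowed and are permitted at the investigator's discretion". For Arm 2, note P to the protocol's prophylaxis schedule of assessments adds: "Switches to the on-demand regimen and between various prophylaxis regimens are allowed at any time at discretion of the investigator".

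SAP 4.4 says treatment modality is recorded at entry, and SAP 4.1 presents results by assigned modality. Neither says where a subject who later switches is counted.

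**The concern.** The numerator and denominator of the prophylaxis rate cover different time. The numerator accrues only while the subject is on routine prophylaxis. The denominator keeps running through on-demand treatment and through surgery, when the normal routine is suspended (protocol 3.2.4). The result is not the rate of use on prophylaxis, which is how a reader of a prophylaxis consumption table would take it.

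In the on-demand table the numerator is unrestricted, so prophylaxis doses given after a switch enter a figure presented as on-demand use.

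Consumption per month and per year, by prophylaxis and on-demand, is a secondary endpoint in all arms (protocol 2.2.2.1). Characterizing it is also a secondary objective for Arm 2 (protocol 2.2.1).

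**Working it through.** The documents state no consumption figure, so there is nothing to reproduce. The check is direct arithmetic.

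**Inputs**
- Formula and denominator: SAP 4.6.2.3 and SAP 4.6.
- f, the share of the evaluation period spent on prophylaxis: not in the documents; assumed 0.25 to 0.90.
- Dose, used only for scale: 30 IU/kg three times weekly (assumed; it lies inside the 15 to 50 IU/kg range that SAP 3.2.1 reports from previous studies).

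**1. Time on both modalities, subject in the prophylaxis table.** Let D be the sum of prophylaxis doses and T the evaluation period in days.

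- SAP figure = D × 365.25 / T
- Rate while on prophylaxis = D × 365.25 / (f × T)
- Ratio = f, whatever the dose, frequency or T

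Rate while on prophylaxis: 30 × 3 / 7 × 365.25 = 4,696 IU/kg per year, or 391 per month.

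| f | SAP, per year | SAP, per month | Understatement |
|---|---|---|---|
| 0.25 | 1,174 | 98 | 75% |
| 0.50 | 2,348 | 196 | 50% |
| 0.75 | 3,522 | 294 | 25% |
| 0.90 | 4,226 | 352 | 10% |

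**2. Surgery, no switch.** Assume a 28-day surgical period in 2 years (730.5 days). The ratio is (730.5 − 28) / 730.5 = 0.962, so 4,516 is reported instead of 4,696, or 3.8% low.

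**3. Subject in the on-demand table who spends half the time on prophylaxis.** Assume one year on-demand with 12 single-dose bleeds at 30 IU/kg, then one year of prophylaxis as above with no bleed treatment.
- On-demand use while on-demand: 12 × 30 = 360 IU/kg per year.
- SAP figure: (360 + 4,696) / 2 = 2,528 IU/kg per year.

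The direction is upward whenever prophylaxis uses more product per unit time than on-demand treatment.

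**4. Switch between prophylaxis frequencies.** Assume 30 IU/kg, one year three times weekly (4,696 IU/kg), then one year twice weekly (30 × 2 / 7 × 365.25 = 3,131 IU/kg).
- All-frequencies row: (4,696 + 3,131) / 2 = 3,913 per year, the correct time-weighted average.
- Frequency rows, if doses are split by frequency while T stays whole: 4,696 / 2 = 2,348 instead of 4,696, and 3,131 / 2 = 1,565 instead of 3,131.

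**5. Effect of the missing classification rule.**

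| Rule | Prophylaxis to on-demand | On-demand to prophylaxis |
|---|---|---|
| Modality at entry | prophylaxis rate too low | on-demand rate too high |
| Final modality | on-demand rate too high | prophylaxis rate too low |

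Neither single-label rule avoids the problem. Each only decides which switchers produce which error.

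**The case against.** The strongest objection is that the denominator may be meant as time on the given regimen. SAP 4.6.2.1 itself speaks of the efficacy evaluation period within an inhibitor status, so the term is not used consistently, and the table shells that might settle it are in a separate document (SAP 5.2). What stands is that the programmed denominator cannot be known from these documents. The reading remains weak, because the SAP names matched time where it wants it: the AsBR derivation uses the treatment time of interest, the ABR requires 8 weeks on the given regimen, and prophylaxis compliance (SAP 4.5.3) uses the cumulative length of prophylaxis periods. The consumption formulas name only the period defined in SAP 4.6.

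A reader might also infer more than the documents support:

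- **That prophylaxis use is understated for every subject who changes regimen.** A change of prophylaxis frequency leaves the all-frequencies row correct. A subject who moves from on-demand to prophylaxis may not be in the prophylaxis table at all if entry modality governs.
- **That one switcher produces both errors.** That requires him to appear in both tables, and no text says he does.
- **That inhibitor periods always dilute the rate.** SAP 3.5.6 says an inhibitor-positive subject may receive intensified prophylaxis, so that time is not necessarily off prophylaxis. SAP 4.6.2.3 also plans a separate consumption analysis while PUPs are inhibitor positive.
- **That the total-dose rows are wrong.** They are valid averages over the whole period; they simply mix modalities.

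Finally, the endpoint is descriptive, and neither the number of switchers nor their division of time is given, so the effect on the summary tables cannot be sized.

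**Conclusion.** The point holds for subjects with time on both modalities. Followed as written, SAP 4.6.2.3 reports f times the on-prophylaxis rate for any such subject in the prophylaxis table: 75% to 10% too low for f between 0.25 and 0.90, a range that is assumed. A switcher kept under on-demand has prophylaxis doses reported as on-demand use. Which error arises depends on a classification rule that the SAP does not state.

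Two lesser effects follow. Surgical time lowers the prophylaxis rate of any subject who has surgery, by about 4% in the assumed case. The three-times-weekly and twice-weekly rows share the problem if doses are split by frequency over the whole period.

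The algebra is exact. The individual IU/kg figures are illustrations, and the shift in the arm-level summaries is unknown.

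**What to change.** In SAP 4.6.2.3, for the prophylaxis and on-demand consumption rows:

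1. Use as denominator the subject's days assigned to that modality (or to that frequency, in the frequency rows), excluding surgical periods.
2. Count only doses given in those days.
3. State that a switcher contributes to each modality for the time spent on it.
4. Keep the existing whole-period total rows and label them as averages over all modalities.

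The cost is a wording change and modest programming. Protocol 3.2.5 requires the eCRF to be updated at each change of regimen, and protocol 3.2.4 asks for the start and end of the surgical period to be recorded, so the dates should be available.

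The downside is that the PTP analysis is already complete (SAP 4.1.2; the list of substantial changes dates the PTP report to November 2019). Apply the change prospectively to the PUP analysis. For PTPs, add a supplementary table on the new definition, or a footnote stating that the reported rates use the whole evaluation period, so that the two sets of figures are not compared as if they were defined alike.

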2.2.2 Secondary Endpoints

2.2.2.1 Efficacy

In **Arm 1 and Arm 3 (PTPs)**, the secondary efficacy endpoints are:

- Annualized bleeding rate (ABR) (traumatic and non-traumatic) during prophylaxis and on-demand treatment.
- Treatment success for bleeding episodes defined as a rating of "excellent" or "good" on the investigator's clinical assessment of hemostatic efficacy 4-point scale.

- Percentage of bleeding episodes requiring 1, 2, 3, or > 3 injections of rVIII-SingleChain to achieve hemostasis.
- Mean actual dose per kg per subject per year; consumption of rVIII-SingleChain, expressed as number of injections and IU/kg per month and per year, as well as IU/kg per event (prophylaxis, on-demand, and surgery).
- Treatment success for surgery, using the 4-point efficacy evaluation of surgical treatment scale.

In **Arm 2 (PUPs)**, the secondary efficacy endpoints are:

- Treatment success for **non-major** bleeding episodes, defined as a rating of "excellent" or "good" on the investigator's clinical assessment of hemostatic efficacy 4-point scale.
- Percentage of bleeding episodes requiring 1, 2, 3 or > 3 injections of rVIII-SingleChain to achieve hemostasis.
- ABR during prophylaxis and on-demand treatment.
- Mean actual dose per kg per subject per year; consumption of rVIII-SingleChain, expressed as number of injections and IU/kg per month and per year, as well as IU/kg per event (prophylaxis, on-demand, and surgery).
- Treatment success for surgery, using the 4-point efficacy evaluation of surgical treatment scale.

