4.2 Subject Withdrawal

4.2.1 Subject Withdrawal

Subjects may withdraw from the study at any time at their own request, or they may be withdrawn at any time at the discretion of the investigator or CSL for safety, behavioral or administrative reasons (eg, due to an AE, protocol violation, subject noncompliance, and study termination).

In accordance with ICH principles of GCP, the investigator always has the option to advise a subject to withdraw from the study if the subject's safety or well-being is compromised by his or her further participation in the study. Concern for the interests of the subject must always prevail over the interests of the study.

If a subject is withdrawn from the study or further participation is declined, they will continue to have access to medical care and will be treated as per routine medical practice.

Arm 2 (PUPs):

In addition to the general withdrawal criteria described above, PUPs in Arm 2 **must be withdrawn** from the study if they develop any of the following withdrawal criteria:

- Use of any FVIII product other than rVIII-SingleChain (or its marketed available version) during the study (including if used as rescue medication).
- Subject develops a confirmed high-titer inhibitor (> 5 BU/mL confirmed by repeat testing at the central laboratory) but is not willing to participate in the **CCI** substudy.
- If the subject in the main study or the **CCI** substudy has successful inhibitor eradication and experiences inhibitor recurrence (relapse; ie, 2 consecutive inhibitor results \geq 0.6 BU/mL after eradication).

Further withdrawal criteria specific to the **CC1** substudy are defined in [Appendix 1](#).

Subjects with a **low-titer** inhibitor may either continue in the main study or can be enrolled into the **CC1** substudy (see [Appendix 1](#)), at the discretion of the investigator after discussion with the sponsor.

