### AsBR

AsBR will be derived by inhibitor status and overall as follows:

$$(\text{number of bleeding events}) / (\text{observed treatment period of interest days}) * 365.25.$$

Only bleeding events requiring treatment will be included in the derivation of bleeding rates. The AsBR will be estimated for subjects who complete at least 8 weeks of treatment on the given inhibitor status using the subject's observed data. If the subject does not complete at least 8 weeks of treatment on the given inhibitor status, then the AsBR will be considered missing.

The number of spontaneous bleeding episodes per year based on a Poisson model and associated 95% CI and the number and percentage of subjects with zero bleeding episodes will be presented. In addition, the rate ratio of Prophylaxis modality to On-Demand modality (Prophylaxis- On-Demand) will be presented, along with the associated 95% CI, as obtained by the Poisson model.

Spontaneous bleeding episodes are those classified as 'Non-traumatic' in e-Diary or 'Spontaneous' in the eCRF. Annualized spontaneous bleeding rate will also be summarized for the following subgroup:

- Positive non-inhibitory Anti-Drug Antibodies (ADAs) and negative during the study
- Age based on age in this study: for PTPs: 0 to < 6 years,  $\geq 6$  to < 12 years,  $\geq 12$  to < 18 years and  $\geq 18$  to  $\leq 65$  years, 0 to <12 years,  $\geq 12$  to  $\leq 65$  years.
- Prophylaxis frequency: every second day, 3 times per week, 2 times per week, other regimen.

In these subgroup analyses rate ratio of Prophylaxis modality to On-Demand modality won't be displayed.

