## **4.6.2 Secondary Efficacy Endpoints**

### **4.6.2.1 Annualized Bleeding Rate**

Annualized bleeding rate, as defined in [Section 4.6.1](#), will be derived also by type of bleed, i.e., for total, spontaneous, traumatic, unknown and joint bleeds for PTPs. Only treated bleeds will be considered. The ABR will be estimated for subjects who complete at least 8 weeks of treatment on the given regimen using the subject's observed data. If the subject does not complete at least 8 weeks of treatment on the given regimen, or has no treated bleeding events while on the given regimen, then the ABR will be considered missing.

A summary of ABR will be performed by inhibitor status if the efficacy evaluation period is greater or equal than 8 weeks on the given inhibitor status.

For PUPs, as secondary efficacy endpoints, annualized bleeding rate, as defined in [Section 4.6.1](#), will be presented also for traumatic, unknown and joint bleeds.

Annualized Bleeding Rates will be derived also separately for the **CCI** Population.

A specific analysis will be produced for annualized bleeding rates while subjects are inhibitor positive on PUPs.

Bleeding events details will be listed while subjects are inhibitor positive and for all subjects.

Subjects < 8 weeks of efficacy assessment will be listed.

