## 4.11 Changes in Conduct or Planned Analyses from the Protocol

Section 2.1 and 2.2: In the protocol, incidence of inhibitor formation to FVIII in Arm 2, PUPs is stated that would be performed on at least 50 PUPs. However, this condition has been removed. Given that patients that develop inhibitors may be withdrawn from the study early, they would not necessarily achieve 50 exposure days but we would definitely have to include them in the calculation. Therefore the text was adjusted to ensure the option to properly report the endpoint regardless of these circumstances.

CCI

Section 3.5.3: Efficacy Population definition has been changed removing the exclusive inclusion of subjects who do not have an inhibitor at any time point during the study.

CCI

Section 4.6.1 and 4.6.2.1: In the Annualized Bleeding Rate analysis it has been added that subjects with an efficacy evaluation period less than 8 weeks (56 days) will be excluded from the analysis to exclude bias due to short evaluation period.

Section 4.6.2.2: The analysis of number of infusions of CSL627 required to achieve hemostasis has been added for completeness of analysis.

Section 4.7.1: Incidence of transient inhibitors has been added for completeness of analysis.

Section 4.7.2.1: Analysis of AESIs has been added for completeness of analysis.

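### SAP 4.6.2.3 annualises each subject's consumption with no minimum observation time, so one short, densely dosed record can materially inflate the mean in small PUP rows, chiefly on-demand

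*SAP*

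**What the plan says.** - **Endpoint.** Protocol 2.2.2.1 names "Mean actual dose per kg per subject per year", with consumption per month and per year, as a secondary efficacy endpoint for PTPs and PUPs. The named quantity is a mean.
- **Formula.** For "Total dose administered per subject per month and per year (IU/kg" and its companion rows, SAP 4.6.2.3 multiplies the subject's sum by 365.25 (per year) or 365.25/12 (per month) and divides by the efficacy evaluation period. No lower limit on that period is stated.
- **Who is included.** "Consumption will be summarized for the Efficacy population and Safety population". Under SAP 3.5.2 and 3.5.3 a single dose is enough to enter (for the Efficacy population, a prophylaxis or on-demand dose).
- **Denominator.** SAP 4.6 starts the period on Treatment Day 1; it "ends at the End of study Visit in this study or the last date of dose, whichever occurs later". Protocol 8.10.6 also places that visit at premature discontinuation.
- **Bleeding rates.** For AsBR: "If the subject does not complete at least 8 weeks of treatment on the given inhibitor status, then the AsBR will be considered missing". For ABR, SAP 4.6.2.1 says: "The ABR will be estimated for subjects who complete at least 8 weeks of treatment on the given regimen". SAP 4.11 gives the reason: subjects with less than 56 days "will be excluded from the analysis to exclude bias due to short evaluation period".
- **Early withdrawal.** SAP 4.12.2 adds no handling that reaches consumption.

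**The concern.** Consumption and bleeding rates are annualised in the same way, so a short denominator affects both. The SAP acts on this for one and gives no reason for leaving the other. Consumption is in one respect more exposed: every included subject has had at least one dose, so a short record always has a positive numerator.

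Arm 2 offers a route to such a record. Protocol 3.1 lets a PUP enter at his first bleed, and the Arm 2 schedules allow Screening and Visit 1 on the same day. Protocol 4.2.1 then requires withdrawal for "Use of any FVIII product other than rVIII-SingleChain (or its marketed available version) during the study", rescue use included. A boy dosed several times at entry and then withdrawn contributes a few days of dense dosing scaled to a year. With a target of 24 PUPs, presented by modality, one such record could dominate the mean and SD of a row.

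**Working it through.** The documents state no consumption figure, so there is none to reproduce. The check applies the SAP formula to assumed records.

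**General result.** Let *n* subjects include one short record with annualised value *x*, and let the others average *m*. The mean becomes ((n−1)m + x)/n, a relative rise of (x/m − 1)/n. It doubles when x ≥ (n+1)m.

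**Inputs**
- From the documents: inhibitor-negative PUPs stay until 75 EDs, expected to take up to 6 years (Protocol 3.3); target of 24 PUPs and at least 200 PTPs (Protocol 11.1); earlier prophylaxis of 15 to 50 IU/kg every second day or 2 to 3 times a week (Protocol 3.2.1).
- Assumed: row sizes, 50 IU/kg per dose, and the length and dosing of the short record. The documents give none of these.

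**On-demand, n = 8, short record of three 50 IU/kg doses in 7 days**
- Short record: 150 × 365.25/7 = 7,827 IU/kg/year.
- Others complete 75 EDs in 2 years: 75 × 50/2 = 1,875. Mean = (7 × 1,875 + 7,827)/8 = 2,619, or +40%. Ratio of totals = (7 × 3,750 + 150)/(14 + 7/365.25) = 1,883.
- Others at 800, which is 75 EDs in 3,750/800 = 4.7 years: mean = (7 × 800 + 7,827)/8 = 1,678, or +110%. Ratio of totals = (7 × 3,750 + 150)/(7 × 4.6875 + 7/365.25) = 804 (810 if the others are observed for only 2 years).
- Doubling needs m ≤ 7,827/9 = 870, so the others must take at least 3,750/870 = 4.3 years to reach 75 EDs. At the full 6 years, m = 625 and the rise is (7,827/625 − 1)/8 = +144%.
- SD: if the other seven were identical, the SD would go from 0 to (x − m)/√n, which is 2,104 for m = 1,875 and 2,484 for m = 800.

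**Sensitivity of the on-demand result**
- Larger row, same record: n = 12 gives +26% (m = 1,875) or +73% (m = 800); n = 24 gives +13% or +37%.
- Longer period: if the same 150 IU/kg were spread over 28 days, x = 150 × 365.25/28 = 1,957. At n = 8 the rise is then 0.5% (m = 1,875) or 18% (m = 800).

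**Prophylaxis, n = 16, short record of five 50 IU/kg doses in 5 days**
- Short record: 250 × 365.25/5 = 18,263.
- Others at 6,500 for 0.6 years (3,900 IU/kg, or 78 doses of 50): mean = (15 × 6,500 + 18,263)/16 = 7,235, or +11%. Ratio of totals = (15 × 3,900 + 250)/(15 × 0.6 + 5/365.25) = 6,518.

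**PTPs, n = 200, others at 3,913** (30 IU/kg 2.5 times a week, assumed)
- A 7,827 record adds (7,827/3,913 − 1)/200 = 0.5%. A record at 100 IU/kg/day (36,525, assumed) adds 4%.

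**The case against.** - **Scale.** A reader might infer that one boy can double mean consumption in any row or arm. The documents do not support that. Doubling needs a small row, a slow on-demand pace among the others and a very short record. If the others finish 75 EDs in 2 years the rise is 40%; in the prophylaxis example it is 11%. This stands and limits the point.
- **Frequency.** A reader might also infer that PUPs commonly enter with a bleed and leave within days. Protocol 3.1 says only that they can enter bleeding or not bleeding, and no text puts the End of Study Visit of a withdrawn boy within days. The scenario is possible; its frequency is unknown.
- **Reach.** SAP 4.1.2 treats the PTP analysis as complete, and Protocol 1.3 reports agreement to stop enrolment. The change therefore serves the PUP analysis only. This stands.
- **Existing safeguards.** Consumption is descriptive. SAP 4.1 also reports SD, median, minimum and maximum, and SAP 4.6.2.1 lists subjects with under 8 weeks of efficacy assessment. These would reveal an extreme value, but they do not correct the mean, which is the named endpoint.
- **Cost of a cut-off.** A 56-day minimum alone would drop early leavers, including boys withdrawn after rescue, although the SAP deliberately summarises consumption in the Safety population. The AsBR and ABR rules are also tied to time on an inhibitor status or regimen, so the rule cannot be copied without naming the period. Both points are fair; the first is why a ratio that keeps everyone must stand beside the restricted mean.

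**Conclusion.** The gap is real: consumption has no minimum period, while the bleeding rates have 56 days for a reason that applies equally here. The effect is confined to small PUP rows, chiefly on-demand. There, one early-withdrawn, densely dosed subject could raise the mean by about 40% to 110% under the stated assumptions (n = 8, 50 IU/kg doses, three doses in 7 days, others at 1,875 or 800 IU/kg/year). The size is conditional and falls quickly with a larger row or a longer period. The median barely moves. No primary endpoint is affected. It is a modest point, worth making because the repair is cheap and follows the SAP's own reasoning.

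**What to change.** In SAP 4.6.2.3, for the PUP analysis:

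1. Report the per-subject monthly and yearly consumption summaries only for subjects with at least 56 days in the period used as denominator: the efficacy evaluation period for the main tables, and inhibitor-positive time for the separate inhibitor-positive analysis.
2. List subjects below that limit with their doses and days, extending the listing already planned in SAP 4.6.2.1.
3. Add by modality a ratio estimate: the sum of IU/kg, IU or infusions over all subjects, divided by total subject-years (and by a further 12 for the monthly figure).
4. Record the change in SAP 4.11.

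The cost is about one sentence and one row per table. The downside is that short records leave the per-subject mean, but they stay in the ratio and the listing. The ratio weights subjects by time observed, so it should be labelled as a different quantity from the mean per subject.
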